## **2. Trial Management**

### **a. List of Participating Enrollment Clinics or Data Collection Centers**

Data will be collected at one site (Medical University of South Carolina, PI: [name].).

### **b. Projected Timetable**

We have conducted a similar study to this one in the past, and thus are familiar with the methods proposed here. We anticipate no issues in adhering to the proposed timeline. Recruitment and data collection will take place over the last half of Year 1 and first half of Year 2. The remaining portion of Year 2 will be used for data collection, data presentation, and manuscript preparation.

### **c. Target Population Distribution**

We plan to enroll 50% men and 50% women. Expected percentages of racial and ethnic groups are 60% White, 30% Black or multiracial, 10% Asian, and 10% Hispanic.

## **3. Data Management and Analysis**

### **a. Data Acquisition and Transmission**

Research materials include questionnaires, expired air samples for analyzing carbon monoxide and breath alcohol levels, urine samples for analyzing nicotine exposure, and urine drug and pregnancy screens. Research data without identifiers will be maintained in a locked file cabinet and on password-protected computers in the research staff workplace, with only alpha-numeric codes identifying subjects. Study consent forms and the linkage between the participants’ names and codes will be stored in a locked file cabinet in a separate location from the study data. All information collected as part of this study will be accessible only to research staff.

### **b. Data Entry Methods**

Some interview and participant-administered questionnaires will be completed on paper. Those data will be entered by the Research Assistant shortly after completion of the assessment. Electronic entries will be verified against the source document by a second Research Assistant.

### **c. Data Analysis Plan**

Data analysis will be completed by [name].

The primary statistical analysis will use linear mixed model with fixed effects for nicotine content, period, and order, and random effects for subject and group. The type-1 error rate will be 0.05. Continuous outcomes will be summarized by the mean, standard deviation, median and range, while categorical outcomes will be summarized by frequencies and percentages. Skewed continuous outcomes will be log-transformed or square root-transformed as appropriate; for example we conventionally analyze cotinine on log scale.

Biomarkers will be analyzed in a natural log scale such that the model assumptions of normality and equal variances can hold, and geometric means in original units will be calculated as well. A p-value < 0.05 would be conventionally used as “statistical significance”.

## 4. Quality Assurance

### a. Procedures in place to ensure the validity and integrity of the data

It will be made clear to participants that all information obtained during assessments is confidential and that no information will be shared with the participants’ clinicians unless the participant requests this in writing. All investigators and staff associated with this project have been trained, and new hires will be trained, on human research ethics in accordance with the requirements of the local institutions during initial project approval.

[name] will train and closely monitor the Research Assistants on the procedures to be used in this study. Such monitoring will consist of frequent in-person discussion of study visits at the beginning of the study and less frequent monitoring as the study progresses. The PI ([name]) will also be present during the Hotel Phase of the experiment, and will discuss any issues with research assistants at least daily.

The first time that participants complete the questionnaires, the Research Assistants will go over the questionnaires to ensure that participants understand the questions. Questionnaires will be reviewed for completeness while the participant is present. Other questionnaires are completed on the computer, so that participants cannot skip a question. Several biochemical measures (expired breath CO, urine pregnancy and drug screens) will be analyzed immediately, while the participant is present. If necessary (e.g., if the sample volume is insufficient for analysis), the Research Assistants can gather another sample immediately and re-analyze.

Data will be collected in a consistent manner across both Hotel Phases of the experiment. Standard operating procedures will be developed. Case report books will be made for to standardize recording. Each visit or Hotel Check In will have a checklist of all measures that need to be obtained and the order by which these measures are administered.

### b. Data collection/entry/transmission/analysis

Many subjective measures will be administered via a data collection website, using electronic forms. These will be identified by Redcap Subject Identifier, which will be generated by Redcap, a participant tracking software system. Biological specimens will be marked with participant ID, transported to the Medical University of South Carolina laboratory suite daily. Smoking topography data will be collected using CReSS handheld topography devices. Data will be analyzed as outlined in Section 3.c. above.

## 5. Regulatory Issues

### a. Reporting of SAEs to the IRB, NIDA and other regulatory authorities

Serious adverse events (SAEs) as defined in 21 CFR 312.32 (death, life-threatening event, new or prolonged hospitalization, persistent or significant disability/incapacity, congenital anomaly/birth defect, immediate medical or surgical intervention) will be reported in an expedited manner to NIDA’s program office, and all applicable regulatory authorities in accordance with the Program’s standard operating procedures. SAEs will be reported to the NIDA program official within 24 hours by phone, fax, and/or email and a written report will

also be submitted to the program official no more than two days later. SAEs that are deaths will be reported to the IRB in 24 hours. Unanticipated problems involving risks to subjects or others will be reported to the IRB within 10 working days after [name] is notified of the event.

### **b. Reporting Changes or Amendments to the Protocol**

Any changes or amendments to the protocol made in response to adverse events/SAEs will be discussed with [name], and then requested in writing to the IRB, which will then grant or deny permission to make the requested change in protocol. NIDA will be informed of any approved changes in protocol by documentation in the noncompetitive continuation application. Changes that significantly alter the scope of the research or the ability of the research to achieve its specific aims will be submitted to NIDA for approval prior to implementation.

### **c. Trial Stopping Rules**

The trial will be stopped if the local IRB recommends trial discontinuation due to SAEs, or if the trial is not progressing due to lack of participant recruitment.

## **6. Trial Safety**

### ***a Potential Risks.***

Risks include breach of confidentiality, issues related to coercion, and risks related to smoking the study cigarettes.

- 6) **Issues Related to Coercion:** Coercion is a possible risk due to monetary compensation for participating in this study. The likelihood of this risk is low because the compensation is commensurate with the amount of time and effort required for this study, as described below under Adequacy of Protection against Risk in the Human Subjects Protection Plan.
- 7) **Survey Questionnaires:** This study will include questions about medical history, drug and alcohol use, and questionnaires about mood. Answering these personal questions could participants uncomfortable.
- 8) **Breach of Confidentiality:** Study data include biological measures of cigarette smoking, pregnancy and illicit drug use. The likelihood of breach of confidentiality is low as we will take precautions to minimize this risk as described below under Adequacy of Protection against Risk.
- 9) **Smoking Cigarettes:** All cigarettes are detrimental to a person's health and can lead to significant medical problems including:
  - h. **Cardiovascular Diseases:** Coronary heart disease, heart attack, stroke, peripheral vascular disease, reduced blood circulation, abdominal aortic aneurysm
  - i. **Respiratory Diseases:** Emphysema, bronchitis, and chronic airway obstruction
  - j. **Cancers:** Cancers of the lung, bladder, cervix, esophagus, kidney, larynx, mouth, pancreas, throat, and stomach; leukemia
  - k. **Other Health Risks Associated with Smoking:** Including but not limited to infertility, lower bone density in postmenopausal women, and hip fracture in women
  - l. **Death**
- 10) **Smoking Study Cigarettes:** Smoking the study cigarettes could cause some minor adverse health effects such as headaches or experience withdrawal symptoms, which are listed below. Due to the altered nicotine levels, there could be a change in cigarette use including the manner in which smoke is inhaled. Participants may also experience increases in levels of carbon monoxide, a gas from smoke.
- 11) **Smoking Withdrawal:** Participants may experience smoking withdrawal symptoms during this study. These symptoms can include anger, irritability, frustration, anxiousness, nervousness, depressed mood or sadness, desire or craving to smoke, difficulty concentrating, increased appetite, hunger or weight gain, insomnia, problems sleeping or awakening at night, restlessness, impatience, constipation, dizziness, coughing, dreaming or nightmares, nausea, and sore throat. These feelings can be uncomfortable but are typically of minimal risk.

- 12) Returning to Regular Smoking:** It is possible that if when participants return to smoking their usual brand of cigarette they may experience mild and transient nausea, dizziness, and lightheadedness.
- 13) Risk to Fetus:** Smoking during pregnancy can lead to miscarriage, preterm delivery, stillbirth, low birth weight, problems with the placenta, birth defects such as cleft palate, sudden infant death syndrome (SIDS), and early childhood behavioral problems.
- 14) Changes in blood pressure and/or heart rate:** Smoking and nicotine can affect the cardiovascular system which may result in changes in blood pressure and/or heart rate.
- 15) Changes in mood, emotions and psychiatric symptoms:** Smoking and nicotine can affect mood and emotions and are associated with psychiatric disorders including major depressive disorder, general anxiety disorder, bipolar disorder and eating disorders. Any changes in nicotine or cigarette consumption could adversely affect mood, emotions and the symptoms related to psychiatric conditions in some individuals.
- 16) Smoking and oral contraceptives in women:** Women who smoke and are over the age of 35 should not take oral contraceptives that contain estrogen without consulting their physician.
- 17) Smoking and medications:** Quitting smoking can greatly benefit participant health. However, changes in smoking can lead to changes in how well some medications work.
- 18) Risk of fire:** Smoking cigarettes inside an enclosed structure (e.g. house, apartment, hotel room) can increase the chances of starting a structural fire. To reduce this risk, participants will be instructed avoid smoking under conditions that might increase the chance of starting a fire (e.g. in bed).

**b Direct Benefits:** There are no immediate benefits from participating in the study. The information obtained from this study may ultimately help the Food and Drug Administration decide how best to regulate tobacco products with the goal of improving public health.

### ***C. Monitoring and Withdrawal of Participants***

#### **Identifying Adverse Events**

While participating in the trial, adverse events and concomitant medications will be assessed at every lab visit and at the end of the Hotel Phase, and expired carbon monoxide will be obtained. Adverse events will typically be identified during the administration of the Health Changes Questionnaire, which will be administered at the end of the Hotel Phase,. Other events may be identified from physiological study measures or by spontaneous reports during non-scheduled assessments. [name] (CO-I) has worked closely with [name] (MD) in handling Adverse Events in the past, and [name] has agreed to be available as needed to discuss adverse events in this study.

#### **Questionnaire items that will be reviewed:**

- Health Changes Questionnaire: If the participant answers '**YES**' to **Questions 1** , the interviewer should administer the 'Adverse Event Form.' The Adverse Event form will ask for additional details about changes in physical and mental health.
  - 1) ***Have you had any negative changes in your physical or mental health that you think might be related to study participation?***

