- 5) **Smoking Study Cigarettes:** Smoking the study cigarettes could cause some minor adverse health effects such as headaches or experience withdrawal symptoms, which are listed below. Due to the altered nicotine levels, there could be a change in cigarette use including the manner in which smoke is inhaled. Participants may also experience increases in levels of carbon monoxide, a gas from smoke.
  - a. **Smoking Withdrawal:** Participants may experience smoking withdrawal symptoms during this study. These symptoms can include anger, irritability, frustration, anxiousness, nervousness, depressed mood or sadness, desire or craving to smoke, difficulty concentrating, increased appetite, hunger or weight gain, insomnia, problems sleeping or awakening at night, restlessness, impatience, constipation, dizziness, coughing, dreaming or nightmares, nausea, and sore throat. These feelings can be uncomfortable but are typically of minimal risk.
  - b. **Returning to Regular Smoking:** It is possible that if when participants return to smoking their usual brand of cigarette they may experience mild and transient nausea, dizziness, and lightheadedness.
  - c. **Changes in blood pressure and/or heart rate:** Smoking and nicotine can affect the cardiovascular system which may result in changes in blood pressure and/or heart rate.
  - d. **Changes in mood, emotions and psychiatric symptoms:** Smoking and nicotine can affect mood and emotions and are associated with psychiatric disorders including major depressive disorder, general anxiety disorder, bipolar disorder and eating disorders. Any changes in nicotine or cigarette consumption could adversely affect mood, emotions and the symptoms related to psychiatric conditions in some individuals.
  - e. **Smoking and medications:** Quitting smoking can greatly benefit participant health. However, changes in smoking rate can lead to changes in how well some medications work.

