#### **Physiological data that will be reviewed:**

- CO level: The 'Adverse Event Form' should be completed if the average CO within any visit or Hotel Check in is:
  - CO is greater than 50 ppm if CO at Screening is < 20 ppm.
  - CO is greater than 60 ppm if CO at Screening is 20 – 34 ppm.
  - CO is greater than 70 ppm if CO at Screening is 35 – 49 ppm.
  - CO is greater than 80 ppm if CO at Screening is 50 – 64 ppm.
  - CO is greater than 90 ppm if CO at Screening is 65 – 80 ppm.

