**Participants will be withdrawn immediate if any of the following occur:**

1. Cardiovascular disease (CVD) event: Typically includes MI (heart attack), PTCA (angioplasty/stenting), bypass surgery, stroke, peripheral vascular disease (arterial blockages in arms or legs leading to procedure or surgery). Less common CVD problems would be new cardiac arrhythmias (e.g., new atrial fibrillation) or new valvular disease) (e.g., mitrial or aortic regurgitation).
2. If they are required to leave the hotel for any reason (e.g., personal, medical)
3. Change in medical or psychiatric status: If a change in medical or psychiatric status as determined by the PI may present previously unrecognized risk to study staff, hotel staff, other participant or self.
4. DVT/PE: deep vein thrombosis/pulmonary embolism, i.e., blood clots in the venous system
5. Suicide Attempt or Ideation: A participant will be withdrawn if he/she attempts suicide or expresses any suicidal ideation at any time during participation in the study.
6. Pregnancy: If a participant indicates she is pregnant, she will be withdrawn from the study, and this event will remain open until delivery. At that time study staff will contact the participant to ask a few questions about the baby's health and will update the open "Adverse Event Form"
7. Expired breath carbon monoxide increase: A participant will be withdrawn from the study if the average of two consecutive readings during the same visit is 100 ppm or greater.

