**Management of SAEs and Other Study Risks**

When an AE occurs, study staff will review the AE with [name] within 24 hours. A study participant may be discontinued from the study if the PI determine it is the best decision in order to protect the safety of a participant. [name] (CO-I) has worked closely with [name] (MD) in handling Adverse Events in the past, and [name] has agreed to be available as needed to discuss adverse events in this study. In the event that a participant either withdraws from the study or the investigator decides to discontinue a participant due to an AE/SAE, the participant will have appropriate follow-up medical monitoring. The participant experiencing an AE/SAE will be followed until the problem resolves, stabilizes, or is clearly unrelated to the study cigarettes.

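### Low-severity, cheap improvement: the questionnaire item that opens the Adverse Event Form covers only health changes the participant thinks might be study-related

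*Combined protocol and SAP*

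**What the plan says.** Under Identifying Adverse Events (Data Safety Monitoring Plan, 6.C), the main route is plain: "Adverse events will typically be identified during the administration of the Health Changes Questionnaire". The same paragraph says that "adverse events and concomitant medications will be assessed at every lab visit and at the end of the Hotel Phase", and that further events may come to light through physiological measures or spontaneous reports.

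The next subsection, on the questionnaire items to be reviewed, gives one item and one rule. The item asks: "Have you had any negative changes in your physical or mental health that you think might be related to study participation". On a YES, the interviewer administers the Adverse Event Form, which asks for further details. No other questionnaire item is shown as opening the form.

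The measures list in section C describes the two versions of the questionnaire more broadly, as covering changes in health since the last visit (V1) or since arrival at the hotel (V2), with no limit to changes linked to the study.

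Under Management of SAEs and Other Study Risks, staff review an adverse event within 24 hours of its occurrence, and a participant with an event "will be followed until the problem resolves, stabilizes, or is clearly unrelated to the study cigarettes".

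**The concern.** The trigger item asks for two things at once: whether there was a negative change, and whether the participant thinks it might be connected with the study. A NO to the second part has the same effect as a NO to the first, and the form that would hold the details is not opened. A participant who sleeps badly and blames the hotel bed, or who has constipation and blames the catered meals, can answer NO truthfully. Insomnia and constipation are both on the protocol's own list of possible withdrawal symptoms (Potential Risks, Smoking Study Cigarettes).

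What is at stake is the completeness of the record of non-serious events. A reader of an adverse event summary could take it to count all negative changes, when its main questionnaire source had already been filtered by the participant's own view of cause.

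**Working it through.** The plan states no figure on this point, so there is none to reproduce. The check is to list every route shown and ask whether it opens a form for one kind of event: a change that is non-serious, is not a CO rise, is not attributed to the study by the participant, and is not volunteered.

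1. **Questionnaire item (6.C).** The participant does not attribute the change, so the answer is NO and no form follows.
2. **CO thresholds (6.C).** The form "should be completed if the average CO within any visit or Hotel Check in is" above limits banded by screening CO. This needs no attribution, but covers CO only.
3. **Pregnancy (6.C).** The participant is withdrawn and "this event will remain open until delivery", with the open form updated then. This needs no attribution, but covers pregnancy only.
4. **Other immediate withdrawal events (6.C).** These are specific: cardiovascular events, clots, suicidality, leaving the hotel, and a change in status that the investigator judges to pose a risk. A minor complaint meets none of them.
5. **Injury (6.C).** It is monitored and may lead to discontinuation. No form is stated for it, and it covers injuries only.
6. **SAE reporting (5.a, repeated in section 6).** "SAEs will be reported to the NIDA program official within 24 hours by phone, fax, and/or email". This applies to serious events only.
7. **Spontaneous reports (6.C).** These are excluded by definition, since the change is not volunteered.
8. **Concomitant-medication assessment (6.C).** This is a scheduled enquiry that needs no attribution and may bring a change to light. No rule shown links it to the form.
9. **Daily review by the investigator (8.b).** It covers the questionnaire, CO and session notes. It may catch a change that staff noticed, but no rule shown makes it open a form, and the questionnaire answer under review may be the filtered one.
10. **Review within 24 hours (Management of SAEs and Other Study Risks).** It starts once an event has been recognised as an adverse event, so it does not find one.

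None of the ten routes, as shown, opens a form for the event defined above. Routes 8 and 9 could still lead to one in practice, so the gap is possible, not certain.

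**Workload of the fix.** The inputs are 20 completers (C1, which says at least 20), 2 stays each (C1), one administration at the end of each stay (6.C) and one lab visit on the morning of each stay (C7b).

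- End of stay only: 20 × 2 × 1 = 40 administrations.
- End of stay plus the lab visit before each stay: 20 × 2 × 2 = 80 administrations.

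Each completer above 20 adds 2 or 4 respectively. These are counts of occasions on which an extra form could arise. They do not count missed events. The documents give no rate at which participants attribute changes to the study, so the number missed cannot be calculated.

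**The case against.** The strongest case on the other side is that this is a preference about question wording with little effect.

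- **The item sets a low bar.** It asks only whether the participant thinks a link is possible. Consent requires that participants understand the risks, so someone told that insomnia may follow is likely to answer YES to it. This stands and narrows the gap, but does not close it.
- **The rule is not stated as exclusive.** Section 6.C says that a YES opens the form. It does not say that nothing else can, and it says in general terms that adverse events are assessed at lab visits and at the end of the Hotel Phase. This also stands. The point is limited to what the shown rules require.
- **The instruments are not reproduced.** The full questionnaire may contain items free of the clause, and part of the measures list is not visible in the public text. Such absences cannot be held against the plan. Even so, the subsection that defines the trigger names one item.
- **Altered drug effects have their own enquiry.** The protocol warns that "changes in smoking rate can lead to changes in how well some medications work". It would be tempting to cite this as a change likely to go unseen, but concomitant medications are assessed on schedule without regard to attribution, so it is a weak example.
- **The follow-up rule is a different matter.** A reader might infer that it contradicts the trigger item, because it lets relatedness be settled after an event is known. It does not. One rule ends follow-up of a recognised event by reference to the cigarettes; the other asks for the participant's impression of study participation. At most, the follow-up rule shows that relatedness can be judged later.

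**Conclusion.** The point holds as a low-severity improvement. Under the rules shown, a non-serious, non-CO change that the participant neither attributes to the study nor volunteers need not lead to an Adverse Event Form. The consequence is a possibly incomplete record of minor events, of unknown size.

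Two stronger readings are not supported. A reader might infer that serious events could be missed through this item, but they have separate expedited reporting that does not depend on it. A reader might also infer differential reporting between conditions, because participants are told the nicotine content of each stay's cigarettes (C5). That disclosure is a deliberate design feature, no attribution rates are given, and neither the outcome lists (C11a; Data Safety Monitoring Plan 1.b) nor the analysis plan (3.c) includes a comparison of adverse events by condition. No bias is shown. Expired CO and the cigarette count do not use the questionnaire, so those outcomes are unaffected.

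The conclusion assumes that the trigger rule is applied as written and that no unseen item or instruction also opens the form.

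**What to change.** Delete the closing clause of the trigger item, which limits it to changes the participant links to the study, so that any reported negative change opens the Adverse Event Form. Have the investigator record relatedness on the form, if it has no such field already.

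The NOTE on the first page says that two changes were implemented for all participants, which suggests that the stays are complete. If so, the item can no longer be changed. Adverse event summaries should then state that the questionnaire trigger was limited to changes participants thought might be study-related.

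The cost is an edit to one item and a short change to the safety plan, or a single sentence in the report. The downside is some extra forms for minor events, from the roughly 40 to 80 administrations counted above.
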